10.2 Lost to Follow-Up

A study participant will be considered lost to follow-up if s/he fails to complete the 6-month outcome assessments and study staff are unable to contact the participant after at least 3 attempts. The following actions must be taken before a participant will be declared lost to follow-up.

- Study staff will attempt to contact the participant, re-send the REDCap survey or reschedule the missed phone-based assessment, counsel the participant on the importance of maintaining the assigned assessment schedule (if necessary), and ascertain whether the participant wishes to and/or should continue in the study
- The study staff will make every effort to regain contact with the participant (using text, email, phone call, and/or alternative means of contact that the participant may have included during the study enrollment process).
- Should the participant continue to be unreachable, s/he will be considered to have withdrawn from the study with a primary reason of lost to follow-up. The participant's data will be retained in study records.

11. Data & Safety Monitoring

11.1 Overview of Data & Safety Monitoring Plan

This research will include a Data and Safety Monitoring Board (DSMB). The DSMB will be convened and managed through the University of Washington's Institute of Translational Health Sciences (UW ITHS).

11.2 Role of the Data & Safety Monitoring Board (DSMB)

The DSMB will review and oversee the following elements:

1. Study enrollment by population (providers/staff, and patients (adults, adolescents))
2. Retention of study participants at 6 months
3. Data completeness and quality
4. Process evaluation data
5. Safety outcomes by intervention and population
6. Decisions related to stopping the trial early due to one or several of the elements above

11.3 Safety Outcomes

This protocol considers completed suicide, suicide attempts, and inpatient admission in the context of highly suicidal study participants as expected events. These will be routinely tracked as key safety outcomes. The following safety outcomes will be assessed for each participant at 3 and 6 months and reviewed by the Data and Safety Monitoring Board twice annually to determine whether the rate of safety outcomes differs by intervention arm:

- Death by suicide
- Attempted suicide
- Interrupted or aborted suicide attempt
- Psychiatric hospitalization for anxiety, depression, and/or suicidal ideation
- Medical hospitalization related to self-harm or attempted suicide
- Medical hospitalization related to unintentional overdose or substance use disorder

11.4 Adverse Events and Serious Adverse Events

This protocol does not include tracking of adverse events (AEs). This protocol does not include real-time tracking of serious adverse events (SAEs) for several reasons. First, as stated above, the most important events that would be defined as SAEs are expected safety outcomes in the context of study participants experiencing suicidality or other forms of mental distress. All deaths of study participants will be reviewed and assessed to determine whether the cause of death is suicide. We do not anticipate any SAEs beyond those listed as safety outcomes above, but unanticipated SAEs that occur will be reviewed by the DSMB and the IRB. Second, this research compares two models of an evidence-based intervention that has been widely studied, has an established safety record, and is already in widespread

clinical practice. This is not an experimental, novel, or untested intervention with unknown safety outcomes. Finally, the most important safety question to ascertain in the context of this trial is whether rates of safety outcomes or SAEs are differential across the two intervention groups. This protocol will monitor safety outcomes collected at 6 months as part of routine study outcome assessments through regular DSMB meetings to ensure equal ascertainment of outcomes across intervention groups. This is the most valid and reliable way to review safety data in the context of this pragmatic clinical trial.

12. Data Collection & Management

12.1 Data Collection

All data for this study will be collected via online REDCap surveys. *Table 2* includes a list of all study variables, which aim they are associated with, and which tool will be used for assessment.

Table 2: MHAPPS Trial Variables & Other Data Elements

Variables			
Outcomes	Tool	Survey Collected	Source
Loneliness	NIH Toolbox – Social Relationship Scales - Loneliness Scale	Aim 1 Survey; Aim 2 Outcome Survey	REDCap
Suicidal ideation & behavior	C-SSRS Screener	Aim 1 Survey; Aim 2 Outcome Survey	REDCap
Recent suicide attempts, suicide completion, & self-harm; lethal means	6-Months Suicide Attempts Survey	Aim 1 Survey; Aim 2 Outcome Survey	REDCap
Perceived Burdenomeness; Thwarted Belongingness	INQ-15	Aim 1 Survey; Aim 2 Outcome Survey	REDCap
Stress	NIH Toolbox – Perceived Stress 10	Aim 1 Survey; Aim 2 Outcome Survey	REDCap
Alcohol and Illicit drug use	Youth Risk Behavior Survey Questions	Aim 2 Baseline Survey; Aim 2 Outcome survey	REDCap
Depression	PHQ-9	Aim 1 Survey; Aim 2 Outcome Survey	REDCap
Anxiety	GAD-7	Aim 1 Survey; Aim 2 Outcome Survey	REDCap
Uptake of outpatient mental health treatment	N/A	Aim 2 Baseline Survey; Aim 2 Outcome Survey	REDCap
Exposure Variables		Survey Collected	Source
Date of birth, age in years, age category (adult/peds)		Aim 1 Survey	REDCap

MHAPPS Trial Protocol

SLHS Applied Research

December 30,2020

Sex at birth	Aim 1 Survey	REDCap
Race and ethnicity	Aim 1 Survey	REDCap
Zip code of residence (urban/rural)	Aim 1 Survey	REDCap
Gender identity & sexuality	Aim 2 Baseline Survey	REDCap
Religion	Aim 2 Baseline Survey	REDCap
Variables related to employment and occupation of self/parent	Aim 1 Survey	REDCap
Education / maternal education	Aim 1 Survey	REDCap
Living situation (permanent, temporary)	Aim 1 Survey	REDCap
Number of people at home	Aim 1 Survey	REDCap
Caregiving for dependent(s)	Aim 1 Survey	REDCap
Financial security and food security	Aim 1 Survey; Aim 2 Baseline Survey	REDCap
Food access and eating habits and COVID-19	Aim 2 Baseline Survey	REDCap
Physical activity and COVID-19	Aim 2 Baseline Survey	REDCap
Perceived risk for COVID-19 & other COVID-19-related questions	Aim 1 Survey; Aim 2 Outcome Survey	REDCap
Masking practices & beliefs	Aim 1 Survey; Aim 2 Outcome Survey	REDCap
Social distancing practices & beliefs	Aim 1 Survey; Aim 2 Outcome Survey	REDCap
School attendance, extracurricular activities	Aim 2 Baseline Survey (Youth)	REDCap
Access to healthcare and mental healthcare services	Aim 2 Baseline Survey; Aim 2 Outcome Survey	REDCap
Domestic violence	Aim 2 Baseline Survey	REDCap
Local COVID-19 prevalence	CDC or Idaho Department of Health & Welfare Prevalence Data	
Process Variables		
Aim 1 proportion of eligible participants completing survey	REDCap	
Aim 2 proportion of eligible participants enrolled	REDCap	

MHAPPS Trial Protocol
SLHS Applied Research
December 30,2020

Participant feedback on phone call (CC+ arm only)	Aim 2 Outcome Survey	REDCap	
Participant feedback on content and timing of caring messages; satisfaction with caring contacts	Aim 2 Outcome Survey	REDCap	
Rating of quality of "connectedness" with participant		Mosio and/or REDCap	
"Dose" of follow-up contact: timing, type (phone vs text), and number of attempted and successful contacts from the Hotline		Mosio and/or REDCap	
"Dose" of Caring Contact text messages: date/time of each text message sent (* 11 text messages)		Mosio and/or REDCap	
Other Variables	Tool	Aim Collected	Source
Does cell phone on record belong exclusively to study participant or is it shared?		Aim 2 Baseline Survey	REDCap
Cell phone number, email address, contract preferences, mailing address, and alternative modes of contact		Informed Consent Form, Aim 1 Survey; Aim 2 Baseline Survey	REDCap
Eligibility and willingness to be contacted about Aim 2 participation		Aim 1 Survey	REDCap
Death		CDC or Idaho State Vital Records	

12.2 Data Management

This study will employ a comprehensive data management plan. The results from the screening and baseline questionnaires (as well as informed consent documents) will be directly entered in REDCap. The patient will be assigned a unique identifier and randomly assigned to one of the two intervention arms immediately following informed consent and study enrollment. Follow-up specialists at the Hotline will review records of new participants and follow-up with patients to initiate the CC+ or CC intervention. Hotline staff will record any attempt at contact or successful contact made.

The statistics team will compile all data for each participant from REDCap on a routine basis for reports and to build and maintain a complete dataset. To protect the confidentiality of participants, data and associated documentation will be available to the PI of the study and key personnel only, under a data-sharing agreement that includes a commitment to: (1) use the data only for research purposes, (2)

secure the data using appropriate computer technology, (3) destroy or return the data after analyses are completed, and (4) not further distribute the data outside specified members of the research team in compliance with SLHS Research data privacy and sharing practices and policy.

The University of Washington Institute of Translational Health Sciences (ITHS) hosts REDCap, a secure, HIPAA-compliant web application, which will be used for building and managing online surveys and databases for this research. ITHS provides REDCap support and an array of research data curation and storage support. Other databases (such as Access, Excel) may be used for study management purposes; all such data will be kept on secured, password-protected computers.

13. Statistical Analysis

13.1 General Analytic Approach

Aim 1: Descriptive statistics will be used to summarize cross sectional survey results as well as baseline demographic and other exposure variables. Linear regression models or generalized linear regression models GLM with robust standard errors will be used to assess the association between variables of interest.

Aim 2: The primary analysis will compare the effectiveness of the two interventions (CC+ and CC) delivered to two populations (patients and providers/staff), potential confounding, effect modification, and mediation will be handled through study design (e.g. use of randomization to assign individuals to interventions), and statistically through stratification (population). Other published studies related to Caring Contacts have shown that patient-centered outcomes such as suicidal ideation change over a 6-month period in response to receipt of these interventions.⁵¹

Analyses will be stratified for patients and providers/staff, modeling the effects of intervention separately in these population groups. There is very little evidence regarding the effect of Caring Contacts on healthcare workers, and we hypothesize that the magnitude of effect may differ by population group. Generating evidence of the effectiveness of Caring Contacts with and without an introductory phone call in healthcare workers is the primary goal of this heterogeneity of treatment effect (HTE) analysis. **Linear regression with robust standard errors will be used to determine whether the primary outcome differs between CC+ vs CC.**

Linear regression and GLM models will be used in the analysis of the secondary outcomes. Robust/sandwich standard errors will be used to allow for departures of the observed standard errors from classic model assumptions.

All data analyses will be completed using appropriate statistical software (such as R and R Studio, SPSS, Stata, SAS, Python, and/or Microsoft Excel). Statistical significance will be determined based on a type I error (alpha) of 0.05 (two-sided). Confidence intervals will be reported in addition to p-values.

Variables will be measured through the Aim 1 survey or Aim 2 Baseline survey and reported using descriptive statistics. Potential effect modifiers will be assessed and include age, sex, gender identity, sexuality, race/ethnicity, religion, employment, urban/rural residence, drug/alcohol use, suicidal ideation at baseline, baseline depression score, baseline anxiety score, baseline stress score, baseline quality of life, measures of socioeconomic status and/or other variables related to the specified outcomes of interest. Data will be analyzed according to both an intention to treat protocol and per protocol received. Please see section 5.4 *Populations for Analyses* for further detail.

This study will report the distribution of key variables to facilitate assessment of the study's internal and external validity. At a minimum, this study will report the distribution of key variables within the analytic population (key variables are defined as those that are included in the causal diagram at the beginning of the *Research Design* section of this Research Plan). Missing data will be assessed on a regular basis through routine data reports. These reports will allow the investigators to assess the cause of missing or anomalous entries, and address these if possible. If missing values cannot be retrieved, the reason for the missingness will be recorded in data comments available through REDCap. Study staff will record the reason for any participant drop-out during the 6 months of follow-up.

[13.2 Power & Sample Size for Aim 2](#)

The total sample size for the aim 2 trial is 660 participants. For each stratum (patients, providers/staff), a sample of 330 subjects (165 in each arm) allows 80% power to detect a difference of 5 units in the primary outcome (loneliness) if a minimum of 70% of participants are retained through study completion.

[13.3 Duplicate Surveys](#)

A data cleaning step will be included to identify surveys completed twice by the same individual. This may occur, for example, when an individual is both a provider/staff person and a patient at SLHS. If duplicate surveys are identified, the first will be retained, and the second will be excluded from the research.

[13.4 Missing Data](#)

Missing data will be tracked and prevented to the extent possible through participant retention measures. When missing data are unavoidable, they will be addressed through statistical analysis. With proper inclusion of variables associated with the probability of missingness, we will assess the nature of missingness; if the missing data follow a 'missing at random' framework, we will use multiple imputation.¹¹³ The most appropriate multiple imputation technique will be determined based on the distributions of missing data and observed variables.¹¹⁴⁻¹¹⁶ Multiple imputation methods incorporate the uncertainty of value estimation into parameter estimates. We will assess the sensitivity of estimates to the imputation approach and variables used in the imputation algorithm.

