1.2 Schema / Study Flow Diagram

Figure 1: MHAPPS Trial Flow Diagram

MHAPPS Trial Protocol

SLHS Applied Research

December 30,2020

2. Research Question & Specific Aims

Research Question: How can health systems support mental health among providers, employees, and patients during the COVID-19 era while minimizing the burden on the health system?

Specific Aims.

- **Aim 1:** Measure the prevalence of mental distress including loneliness, anxiety, depression, substance use, suicide ideation and other suicide-related risk factors in providers, staff, and patients served by SLHS. Describe differences associated with age, sex, race, ethnicity, urban or rural residence, living situation, occupation, local COVID-19 prevalence, perceived risk related to COVID-19, and masking and social distancing practices.
- **Aim 2:** Compare the effectiveness of two versions of the Caring Contacts intervention ((1) introductory phone or video call (phone call) followed by text messages (CC+), versus (2) text messages alone (CC)) to reduce loneliness and improve mental health outcomes among SLHS patients, providers, and staff experiencing mental distress during the COVID-19 era.
 - **Aim 2 Hypothesis:** We hypothesize that including an introductory phone call with the Caring Contacts intervention will yield better mental health outcomes among providers, staff, and patients experiencing mental distress than a Caring Contacts intervention with no introductory phone call.

3. Introduction

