Local COVID-19 prevalence and perceived risk related to COVID-19 may influence the protective health behaviors an individual engages in during the pandemic. The experience of mandatory closures of schools, businesses, and other facilities will likely vary for participants in “hot-spot” areas such as Ada, Canyon, or Blaine counties.^{91,92} Additionally, The higher and individual perceives their infection risk to be, the more likely they are to engage in **social distancing** and handwashing to protect from COVID-19.⁹³

Measuring masking and social distancing beliefs and practices of respondents will be key to understanding the protective behaviors of participants and the degree of increased isolation experienced during the pandemic. Masking has been shown to be an effective measure to reduce the spread of COVID-19.⁹⁴⁻⁹⁶ Despite calls from SLHS and other agencies for universal mask wearing in Idaho,⁹⁷ a state-wide mask order has not been issued. While social distancing orders were implemented,⁹¹ varying degrees of adherence⁹⁸ may influence the impact of those orders on mental health.

Gender identity and sexuality are strongly associated with risk of suicidal ideation and behavior. **Lesbian, gay, bisexual, transgender, or gender-nonconforming (LGBTQ+)** individuals are two to seven times more likely than straight, cisgender peers to attempt suicide.³³⁻³⁸

Religious affiliation is associated with suicidality, but the magnitude and direction of that association differs depending on the religion and its intersection with socio-cultural factors (e.g., sexuality). A recent meta-analysis found that **religiosity protects against suicidal completion**, with a pooled odds ratio of 0.38 (95% CI: 0.21-0.71).³⁹ Another review found that 75% of published studies identified religion as protective against suicidal ideation and behavior.⁴⁰

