2 SPECIFIC AIMS

Aim 1: Measure the prevalence of mental distress including loneliness, anxiety, depression, substance use, suicide ideation and other suicide-related risk factors in providers, staff, and patients served by SLHS. Describe differences associated with age, sex, race, ethnicity, urban or rural residence, living situation, occupation, local COVID-19 prevalence, perceived risk related to COVID-19, and masking and social distancing practices.

[figure not shown]
Aim 2: Compare the effectiveness of two versions of the Caring Contacts intervention ((1) introductory phone or video call (phone call) followed by text messages (CC+), versus (2) text messages alone (CC)) to reduce loneliness and improve mental health outcomes among SLHS patients, providers, and staff experiencing mental distress during the COVID-19 era.

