4 DATA SOURCE

All data for this study will be collected via online REDCap surveys. *Table 1* includes a list of all study variables, which aim they are associated with, and which tool will be used for assessment.

Table 1: MHAPPS Trial Variables & Other Data Elements

Variables			
Outcomes	Tool	Aim Collected	Source
Loneliness	NIH Toolbox – Social Relationship Scales - Loneliness Scale	Aim 1	REDCap
Suicidal ideation & behavior	C-SSRS Screener	Aim 1	REDCap
Recent suicide attempts, suicide completion, & self-harm; lethal means	6-Months Suicide Attempts Survey	Aim 1	REDCap
Perceived Burdensomeness; Thwarted Belongingness	INQ-15	Aim 1	REDCap
Stress	NIH Tool Box – Perceived Stress 10	Aim 1	REDCap
Alcohol and Illicit drug use	Youth Risk Behavior Survey Questions	Aim 2	REDCap
Depression	PHQ-9	Aim 1	REDCap
Anxiety	GAD-7	Aim 1	REDCap
Uptake of outpatient mental health treatment	n/a	Aim 2	REDCap
Exposure (Baseline)	Tool	Aim Collected	Source
Age in years, age category (adult/peds)	Baseline Survey	Aim 1	REDCap
Sex	Baseline Survey	Aim 1	REDCap
Race and ethnicity	Baseline Survey	Aim 1	REDCap

Address including Zip code of residence (urban/rural)	Baseline Survey	Aim 1	REDCap
County of residence (urban/rural)	Baseline Survey	Aim 1	REDCap
Gender identity & sexuality	Baseline Survey	Aim 2	REDCap
Religion	Baseline Survey	Aim 2	REDCap
Occupation	Baseline Survey	Aim 1	REDCap
Education	Baseline Survey	Aim 1	REDCap
Living Situation (permanent, temporary)	Baseline Survey	Aim 1	REDCap
Number of People at Home	Baseline Survey	Aim 1	REDCap
Perceived Risk for COVID-19	Baseline Survey	Aim 1	REDCap
Masking Practices	Baseline Survey	Aim 1	REDCap
Social Distancing Practices	Baseline Survey	Aim 1	REDCap
Domestic Violence	Baseline Survey	Aim 2	REDCap
Local COVID-19 Prevalence			CDC or Idaho Department of Health & Welfare Prevalence Data
Process Variables		Source	
Aim 1 proportion of eligible participants completing survey			REDCap
Aim 2 proportion of eligible participants enrolled			REDCap
Participant feedback on phone call (CC+ arm only)			REDCap
Participant feedback on content and timing of caring messages			REDCap
“Dose” of follow-up contact: timing, type (phone vs text), and			Mosio

number of attempted and successful contacts from the Hotline		
“Dose” of Caring Contact text messages: date/time of each text message sent (* 11 text messages)		Mosio
Other Variables	Tool	Source
Does cell phone on record belong exclusively to study participant or is it shared?	Baseline Survey	REDCap

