7.1.2 Association of COVID attitudes, beliefs, and practices with outcomes

Linear regression models or generalized linear regression models (GLM) with robust standard errors will be used to assess the association between the primary and secondary outcomes and COVID attitudes, beliefs, and practices, adjusting for baseline demographic information. Each outcome will be modeled separately.

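### Local COVID-19 prevalence is an area-level Aim 1 factor with no stated provision for clustering by area, so its intervals will be too narrow unless residual within-area correlation is near zero

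*Protocol*

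**What the plan says.** **The aim.** Protocol Section 2 lists, among the Aim 1 factors, "local COVID-19 prevalence, perceived risk related to COVID-19, and masking and social distancing practices". SAP Section 2 repeats the aim: "Describe differences associated with age, sex, race, ethnicity, urban or rural residence, living situation, occupation, local COVID-19 prevalence".

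**The source.** Protocol 12.1, Table 2 gives the source of local prevalence as "CDC or Idaho Department of Health & Welfare Prevalence Data"; SAP Section 4, Table 1 gives the same source. It is not a survey item. No geographic unit or time window is fixed. The rationale in Protocol 8.1.1 speaks of hot-spot "areas such as Ada, Canyon, or Blaine counties", which points to county. SAP Table 1 lists county of residence as a baseline item; Protocol Table 2 lists zip code.

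**The model.** Protocol 13.1 has one sentence for all Aim 1 associations: "Linear regression models or generalized linear regression models GLM with robust standard errors will be used to assess the association between variables of interest". Where 13.1 explains the purpose of such errors, for the secondary outcomes, the purpose is general: "Robust/sandwich standard errors will be used to allow for departures of the observed standard errors from classic model assumptions". SAP 7.1.2 models outcomes against "COVID attitudes, beliefs, and practices, adjusting for baseline demographic information", and SAP 7.1.3 models them against employee category. Neither names local prevalence. No section mentions a cluster variable, a random effect or a correction for few clusters.

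**Size and threshold.** The Protocol plans about 4,800 Aim 1 respondents (2,400 patients and 2,400 providers and staff); SAP Section 5 says up to 4,000. Recruitment lasts 6 months. Protocol 13.1 sets a two-sided alpha of 0.05, with confidence intervals reported alongside p-values.

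**The concern.** When an exposure is constant within an area, the information about it comes mainly from differences between areas. Distress may also differ between areas for other reasons, and the Protocol suggests some: Protocol 8.1.1 expects the experience of closures to vary in hot-spot counties, notes uneven adherence to distancing orders, and links rural residence to worse health. Adjusting for respondents' demographics need not remove such differences.

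A sandwich estimator that sums over individuals allows for unequal variances but treats respondents as independent. If neighbours' residuals are positively correlated, it understates the standard error of a shared exposure. A chance difference between areas could then be reported as an association with local prevalence. What is at stake is one of the associations promised under Aim 1.

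**Working it through.** The documents state no precision or power for Aim 1, so there is no planned figure to reproduce. The check asks how far an unclustered robust interval could be wrong.

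**Inputs from the documents.** N = 4,800 (Protocol) or 4,000 (SAP); 2,400 if patients and staff are modelled separately; nominal two-sided 5%.

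**Inputs assumed, because the documents do not give them.** K areas of equal size (44 or 20), and a residual ICC after covariate adjustment of 0 to 0.02.

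**Formulas**, for an exposure constant within area:
- respondents per area: m = N / K
- design effect: DE = 1 + (m − 1) × ICC
- true SE / reported SE = √DE
- actual coverage of a nominal 95% interval = 2Φ(1.96/√DE) − 1

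**Worked case.** N = 4,800 and K = 44 give m = 109.09. At ICC 0.01, DE = 1 + 108.09 × 0.01 = 2.08 and √DE = 1.44. Coverage = 2Φ(1.96/1.44) − 1 = 82.6%.

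For N = 4,800 and K = 44:

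| ICC | DE | True SE / reported SE | Coverage |
|---|---|---|---|
| 0 | 1.00 | 1.00 | 95.0% |
| 0.001 | 1.11 | 1.05 | 93.7% |
| 0.005 | 1.54 | 1.24 | 88.6% |
| 0.01 | 2.08 | 1.44 | 82.6% |
| 0.02 | 3.16 | 1.78 | 73.0% |

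Coverage under other assumptions:

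| N, K | m | ICC 0.001 | 0.005 | 0.01 | 0.02 |
|---|---|---|---|---|---|
| 4,800, 20 | 240 | 92.2% | 81.4% | 71.3% | 58.5% |
| 4,000, 44 | 90.9 | 94.0% | 89.6% | 84.5% | 75.9% |
| 2,400, 44 | 54.5 | 94.4% | 91.8% | 88.6% | 82.7% |

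**Simulation check** (600 runs per setting, N = 4,800, K = 44, individual-level robust errors; Monte Carlo SE about 1 to 2 percentage points):
- Equal areas: coverage 94.5%, 93.0%, 88.7%, 80.2% and 72.7% at ICC 0, 0.001, 0.005, 0.01 and 0.02, in line with the formula.
- Unequal areas: 69.0% at ICC 0.01 and 58.0% at 0.02.
- Half the exposure variance month to month within area: 88.8% at 0.01 and 81.7% at 0.02.

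**Is plain clustering enough?** With uncorrected area-clustered errors and a t reference on K − 1 degrees of freedom, coverage at ICC 0.01 was 91.7% with equal areas and 85.3% with unequal areas. At ICC 0 with equal areas it was 91.3%, below the 94.5% of the unclustered errors. Naming a cluster without a small-sample correction therefore repairs only part of the problem, and costs some coverage where no problem exists.

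**The case against.** Five arguments run the other way.

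- **The text says robust, not individual-level.** Sandwich errors include the cluster-robust form, so a reader who infers that the plan chose individual-level errors goes beyond the wording. That stands. The unclustered reading is nonetheless the natural one: 13.1 also prescribes robust errors for the individually randomized Aim 2 comparison, and a cluster-robust analysis needs a named cluster.
- **The SAP does not say that local prevalence will be modelled.** It appears there only in the aim and the data table, and the aim is worded as description. That stands too. It leaves the Protocol's general sentence as the only rule for an association that both documents promise.
- **The undercoverage is conditional.** It needs a residual ICC above zero, and the ICC, the number of areas and the geographic unit are all missing. At ICC 0.001 with 44 equal areas the loss is about one percentage point. That stands, and it rules out saying flatly that the intervals are too narrow.
- **Prevalence can change over 6 months of recruitment.** Variation within areas adds information. In simulation this reduced the loss but did not remove it.
- **The scope is small.** This is one factor among about eleven in a cross-sectional survey with no stated power. That stands and limits the priority.

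**Conclusion.** The point holds as a conditional one. Local prevalence is shared within areas, the only rule that covers it makes no provision for that, and on its natural reading the rule understates uncertainty whenever the residual within-area ICC is above zero. With 4,800 respondents and 44 equal areas, coverage falls from 95% at ICC 0 to 73% at ICC 0.02; with 20 areas it is 58.5% at ICC 0.02. These figures rest on assumed area counts and ICCs, equal areas, and prevalence fixed over time within each area.

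A reader might infer that this association is bound to be declared significant far too often. With 20 to 44 areas and ICC 0.005 to 0.02, the false-positive rate of a nominal 5% test would be 11% to 42% (100% minus coverage). The documents do not establish that range, and near ICC 0 the excess disappears.

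A reader might also extend the concern to the trial. Aim 2 randomizes individuals, and its primary model (SAP 7.2.1) compares arms adjusting for the baseline score; local prevalence is not in it. The consequence is confined to this Aim 1 association.

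**What to change.** Add to SAP 7.1, with a matching clause in Protocol 13.1, that any model containing local COVID-19 prevalence will:

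1. link prevalence to each respondent by a named area unit and by survey date, over a stated time window. County is a workable unit because SAP Table 1 already lists it; the Protocol table would need the same item, or a rule for deriving county from zip code.
2. use standard errors clustered on that area with a small-sample correction (CR2 or wild cluster bootstrap), or a random area intercept.

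Report the number of areas and the estimated ICC with the result.

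The cost is a few lines of text, a decision on unit and window that any use of this variable needs anyway, and a software option. No further participants are needed. The downside is a somewhat wider interval for this one exposure: by √DE, about 1.05 to 1.78 times for 4,800 respondents in 44 equal areas at ICC 0.001 to 0.02.
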